1.2 Rationale and hypothesis

Thousands of patients undergo ventral hernia surgery each year. Quadratus lumborum blocks are a relatively new approach for providing analgesia to the abdominal wall. The effectiveness of quadratus lumborum blocks in reducing pain, opioid consumption, and time to discharge has not been evaluated for this surgery. We propose a prospective, single-center, randomized trial to evaluate the impact of quadratus lumborum block on patient recovery profile when performed for laparoscopic ventral hernia repair compared to a standard medical management. Standard medical management typically includes perioperative multimodal analgesia utilizing acetaminophen, opioids, non-steroidal anti-inflammatory drugs, and dexamethasone. Peripheral nerve blocks, as are offered in our study, are typically offered to patients but are not routinely performed secondary to time constraints in the operating room and surgeon or patient preference. The primary outcome of the study is pain at rest on POD1. Secondary outcomes will include pain at rest on POD 0, 2 and 7, pain with activity on POD 0, 1, 2 and 7; opioid consumption on POD 0, 1, 2 and 7; nausea in PACU; time to hospital discharge and patient satisfaction.

2. Objectives

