2.1 Primary outcome and endpoint

The primary outcome in this study will be pain scores as assessed by the 11-point numeric rating scale on POD 1.

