2.2 Secondary outcomes and endpoints

The secondary outcomes of this study are to compare the following perioperative variables:

Preoperative Variables:

- Baseline pain

Intraoperative Variables:

- Opioid consumption
- Additional analgesics
- Anti-emetic administration

PACU Variables:

- Pain at rest
- Pain with activity
- Nausea
- Numbness distribution
- Opioid consumption
- Time in PACU (duration)
- Time to discharge home (duration)
- Location of most severe pain

POD 1, 2, and 7 Variables:

- Pain at rest

- Pain with activity
- Opioid consumption in morphine equivalents
- Nausea necessitating treatment
- Location of most severe pain
- Satisfaction with perioperative care

3. Study design

This study is a prospective, single-center, randomized trial in which 48 subjects will be enrolled at the University of Wisconsin Hospitals and Clinics (UWHC). The details of the power analysis can be found below. These subjects must meet study eligibility criteria and be scheduled to undergo an elective laparoscopic ventral hernia repair. These subjects must also agree to undergo quadratus lumborum block for postoperative analgesia. Patients will be randomized to receive QLB in addition to medical management or medical management alone. Recovery characteristics, including pain scores, nausea, opioid consumption, duration of time in PACU and to discharge, will be evaluated.

4. Study population

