7.2 Subject withdrawals

At any point prior to or during the intervention period, the subject's clinical care team or a study physician may decide the subject should be withdrawn from the study. Additionally, a subject may at any point elect to withdraw themselves from the study. If a subject is withdrawn from the study for any reason the subject will then be followed according to standard of care follow-up.

Study intervention will immediately stop and subject's clinical care team and a study physician will be immediately notified if the subject suffers a severe adverse perioperative outcome.

In the event the study method is terminated, the reason for termination will be documented on a case report form.

8. Data analysis and statistical considerations

All data will be summarized using standard descriptive statistics, including mean, standard deviation, minimum, maximum, median, inter-quartile range, and confidence intervals, as appropriate. The data will be presented graphically (where possible) using scatter plots, profile plots, or histograms. Data analyses will be performed on an intent-to-treat basis based upon assignment to a treatment arm using SAS (SAS Institute Inc., Cary, NC; version 8.2 or greater) or other statistical software. The primary analysis will consist of comparing the two groups for superiority. For all tests, statistical significance will be defined as a p-value less than 0.05. Repeated measures ANOVA will be used to analyze comparisons made across multiple time points. Patients with missing longitudinal data will be handled by either using data imputation methods to replace the missing data or via alternative analyses tolerant of missing data values. Holm-Bonferroni correction will be used to control familywise error rates for comparisons across multiple time points.

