8.1 Sample size determination

The primary outcome for this study will compare resting NRS pain scores on POD1 between the QLB and medical management groups. A previous study of laparoscopic ventral hernia surgery reported an average POD1 pain score of 4.5 +/- 2.2 NRS (Fields et al, 2015). This average pain score is in keeping with our experience with patients after having laparoscopic ventral hernia surgery at UW-Madison. We feel that a reduction in pain of 2 NRS on POD1 would be meaningful for patients and their physician teams. Therefore, we will power this study to an effect size of 2 NRS. We will accept a type 1 error rate of 0.05 and 80% power. Using these metrics, the study will require a sample size of 21 patients in each group to

detect a statistical difference. To account for patients dropping out or not completing the study, we will enroll 24 patients in each group for a total of 48 patients.

9. Risks and benefits of trial participation

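### Does listing POD1 rest pain again among the secondary variables pull the primary comparison into the Holm correction?

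*Combined protocol and SAP*

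**What the plan says.** - **Primary outcome.** Section 1.2: "The primary outcome of the study is pain at rest on POD1". Section 8.1 agrees: "The primary outcome for this study will compare resting NRS pain scores on POD1 between the QLB and medical management groups". Section 2.1 gives the same scale and day but does not specify rest: "The primary outcome in this study will be pain scores as assessed by the 11-point numeric rating scale on POD 1".
- **Secondary outcomes, Section 1.2.** "Secondary outcomes will include pain at rest on POD 0, 2 and 7, pain with activity on POD 0, 1, 2 and 7". POD1 is absent for rest pain and present for activity pain.
- **Secondary outcomes, Section 2.2.** The list opens with "The secondary outcomes of this study are to compare the following perioperative variables" and is arranged by stage: preoperative, intraoperative, PACU, then "POD 1, 2, and 7 Variables". Rest pain is the first item under that last heading, so POD1 rest pain appears among the secondaries.
- **Multiplicity, Section 8.** The primary analysis is a superiority comparison of the two groups, and every test uses a threshold of 0.05. Repeated measures ANOVA is assigned to comparisons over several time points, and "Holm-Bonferroni correction will be used to control familywise error rates for comparisons across multiple time points". The family is not listed.
- **Sizing, Section 8.1.** "We will accept a type 1 error rate of 0.05 and 80% power", with a difference of 2 NRS points and an SD of 2.2. This gives 21 per group, raised to 24 per group for dropout.

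**The concern.** One comparison carries two labels, and the labels can carry different significance rules. As the sole primary, POD1 rest pain is tested at 0.05. If the Section 2.2 list were taken as the Holm family for rest pain (PACU, POD 1, POD 2, POD 7), the smallest of four p-values would have to fall below 0.05/4 = 0.0125, the next below 0.05/3 = 0.0167, and so on. A POD1 p-value of 0.03 would then be positive under Sections 1.2 and 8.1 but could be negative under Section 2.2. Section 8 does not expressly exempt the primary. Two things would be at stake: power below the stated 80%, and a choice between readings made after the p-value is known.

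**Working it through.** **Inputs.** From Section 8.1: difference 2, SD 2.2, alpha 0.05, power 80%, 21 evaluable and 24 enrolled per group. From Section 5: 1:1 allocation. Assumed: a two-sided test, since the documents do not state sidedness.

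**Step 1: reproduce the plan's figure.** Standardised difference d = 2/2.2 = 0.909. The normal approximation gives n = 2 × (1.960 + 0.842)² × (2.2/2)² = 19.0, so 19 per group. The t test has noncentrality d × √(n/2) and 2n − 2 degrees of freedom:

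- n = 20: power 79.997%, just short of 80%.
- n = 21: noncentrality 0.909 × √10.5 = 2.946, df 40, critical value 2.021, power 82.0%.

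The smallest n that reaches 80% is therefore 21, as stated. A one-sided test would need only 15 (normal) or 16 (t), which supports the two-sided assumption. Enrolling 24 allows for 1 − 21/24 = 12.5% dropout.

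**Step 2: see which alpha the plan's figure implies.** The t-test sample size at 0.05/m is:

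| m | alpha | n per group for 80% |
|---|---|---|
| 1 | 0.05 | 21 |
| 2 | 0.025 | 25 |
| 3 | 0.0167 | 27 |
| 4 | 0.0125 | 29 |

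Of these, only the unadjusted level returns 21. Section 8.1 was therefore calculated with the primary standing alone.

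**Step 3: power with the primary outside the Holm family.** At alpha 0.05, power is 82.0% at 21 per group. At 24 per group (noncentrality 0.909 × √12 = 3.149, df 46, critical value 2.013) it is 86.9%. The stated 80% holds.

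**Step 4: power if the primary were inside a four-time-point family.** At the first Holm step (0.0125) power is 63.0% at 21 per group and 70.7% at 24. The full Holm procedure was simulated with 40,000 trials per scenario. The between-visit correlations (0.3 / 0.7) and the effect patterns are assumptions, because the documents give neither:

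| Effects at PACU, POD1, POD2, POD7 | 21 per group | 24 per group |
|---|---|---|
| 0, 2, 0, 0 | 63.3% / 62.9% | 70.8% / 70.7% |
| 2, 2, 1, 0 | 66.2% / 65.1% | 74.0% / 73.2% |
| 2, 2, 2, 2 | 73.8% / 71.9% | 81.2% / 79.1% |

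In these simulations the two readings gave different POD1 verdicts in 8-19% of trials at 21 per group and 6-16% at 24 with a true 2-point effect, and in about 3.5% with no effect.

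**Step 5: decide which reading the text supports.**

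- Section 1.2 drops POD1 from the secondary list for rest pain but keeps it for activity pain. That looks deliberate.
- Section 8 describes the primary comparison separately and links Holm, like the repeated measures ANOVA, to comparisons over several time points. A two-group comparison on one day does not naturally fall under that phrase.
- Section 2.2 groups variables by when they are collected. It includes baseline pain, which is recorded before treatment and cannot be a treatment outcome, and it does not mention multiplicity. One heading covers all six items recorded for POD 1, 2 and 7.
- The four-member family in Step 4 is set out nowhere. It has to be built by joining the PACU sub-list to the POD 1, 2 and 7 sub-list.

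The figures in Step 3 therefore describe the plan as written. Those in Step 4 describe a reading that the plan does not support.

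**The case for a change.** The best case for a change is that a pre-specified plan should not rely on inference. The duplicate is in current text. Section 1.2 introduces its secondaries as a list that may not be complete, but that does not explain naming the primary again as a secondary. Rest pain is measured at several times, so POD1 is literally one of them, and Section 8 never states that the primary is exempt. Section 8 also leaves open whether the POD1 comparison comes from the repeated measures model. If the result were p = 0.03, a decision taken then to leave the primary outside the correction could look driven by the data, and a short edit would prevent that.

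What stands is that the duplicate and the silence are both real, and that the power loss would not be trivial if the primary were inside the family. What does not follow is that the outcome is open. The primary is named in two sections, and the trial is sized on it at an unadjusted 0.05, a choice recorded before any data. An analyst who tests POD1 at 0.05 is following the plan. Fuller wording that fixed two-sidedness and a separate Holm family within each secondary outcome would go beyond reconciling the text. Those are reasonable design choices, but the documents do not make them and they are for the sponsor.

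**Conclusion.** No change to the plan is needed. The repeat in Section 2.2 is a clerical duplicate in a list arranged by visit, and the silence in Section 8 is a gap that Sections 1.2 and 8.1 lead any analyst to fill the same way: POD1 rest pain is tested alone at 0.05, and Holm applies to the comparisons over time among the secondaries. On that reading the stated sample size and power are right (82.0% at 21 per group and 86.9% at 24, assuming a two-sided t test with difference 2 and SD 2.2). Either reading controls the type 1 error, so no false-positive risk depends on the point. The lower figures (about 63-74% at 21 and 71-81% at 24) are conditional on a disfavoured reading and on assumed correlations and effects, and should not be quoted as the power of this trial. If the document is revised for other reasons, marking POD1 rest pain in Section 2.2 as the primary and saying in Section 8 that it lies outside the Holm correction would be a helpful courtesy. The membership of the secondary Holm families is for the sponsor to define.

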8.1 Sample size determination

The primary outcome for this study will compare resting NRS pain scores on POD1 between the QLB and medical management groups. A previous study of laparoscopic ventral hernia surgery reported an average POD1 pain score of 4.5 +/- 2.2 NRS (Fields et al, 2015). This average pain score is in keeping with our experience with patients after having laparoscopic ventral hernia surgery at UW-Madison. We feel that a reduction in pain of 2 NRS on POD1 would be meaningful for patients and their physician teams. Therefore, we will power this study to an effect size of 2 NRS. We will accept a type 1 error rate of 0.05 and 80% power. Using these metrics, the study will require a sample size of 21 patients in each group to

detect a statistical difference. To account for patients dropping out or not completing the study, we will enroll 24 patients in each group for a total of 48 patients.

9. Risks and benefits of trial participation

9.1 Potential risks

Standard of care is currently for patients presenting for ventral hernia repair to receive medical management without a regional anesthetic technique although it is reasonable and clinically accepted to offer truncal blocks, such as the QL block, in patients whom it is suspected will be challenging in terms of their pain control or may be particularly sensitive to opiate narcotics. Patients in the control arm face no additional risk. For patients in the intervention arm, risks for quadratus lumborum blockade involve bleeding, infection, and nerve damage at the site of injection. Risks associated with the use of bupivacaine include allergic reaction or inadvertent intravascular injection. Other adverse reactions such as nausea, vomiting, and constipation are possible. All of these adverse effects are extremely rare.

Risks associated with loss of confidentiality

There is a risk that information recorded about subjects will be shared with people who would not normally have access to this information.

Unknown risks

This study may involve risks to the subject which are currently unforeseeable. We will inform subjects as soon as possible if we discover any information that may affect the subject's health, welfare, or decision to be in this study.

9.2 Mitigation of potential risks

Regarding QLB: The risks of QLB will be minimized by carefully controlling the dose of bupivacaine and performing the block under ultrasound guidance allowing visualization of local anesthetic spread and avoiding intravascular injection. These procedures are performed under the supervision of an anesthesiologist that has subspecialized in regional anesthesia. The standard of care includes sterilizing the field of the block, using sterile equipment including gloves and needles to minimize the risk of infection. Ultrasound guidance allows us to identify all important adjacent structures during the procedure to avoid injury to adjacent tissue and blood vessels. In general, complications from peripheral nerve blockade such as the QL block are very rare.

Regarding Pain: The risk of inadequate analgesia will be minimized by the availability of supplemental oral and intravenous analgesics.

Confidentiality will be protected to the extent possible, by coding subject data and storing electronic data on a password-protected anesthesiology department network computer and hard copy data (source documents, signed consent forms, CRFs) in a locked study office.

9.3 Potential benefits and risk-to-benefit ratio

While there are risks to involvement in this research trial, they generally should be infrequent and not difficult to manage. The potential benefits of this research could result in improved pain control with decreased need for opioid medications. Additionally, patients may be able to return to their normal activities more quickly.

10. Adverse events and unanticipated problems

10.1 Adverse event definitions

Adverse event (AE)

An adverse event is defined as any untoward or unfavorable medical occurrence in a human subject including any abnormal sign, symptom, or disease temporally associated with the QLB or study procedure that appears or worsens during the study or study follow-up period. AEs may be anticipated (e.g., redness/soreness at injection site) or unanticipated (e.g., bleeding/infection/nerve damage).

Adverse event information will be collected throughout the study from informed consent through resolution of the AE and documented on the case report form or the standard follow-up questionnaire.

All AEs (anticipated and unanticipated) will be recorded on one of the study data sheets (case report form or standard questionnaire) by a study investigator or study staff. In the event of an unanticipated AE, the primary anesthesia team caring for the subject will intervene as deemed appropriate. These are the same provisions that would be made for any non-study case and represents standard practice.

Serious adverse event (SAE)

A serious adverse event is defined as any adverse event that meets one of the following criteria:

- Results in death; OR
- Is life-threatening; OR
- Requires hospitalization or prolongs existing hospitalization; OR
- Results in significant or persistent disability or incapacity; OR
- Results in a congenital anomaly/birth defect.

Given the minimal risk associated with the performance of QLB and the study procedures, no serious adverse events (SAEs) are anticipated. If a SAE occurs, the study primary and co-primary investigators will be immediately notified and further enrollment in the study will be halted until a full explanation of the cause of the event and its relationship to the QLB and/or study procedure is understood. The IRB will be notified and re-initiation of study enrollment will not occur until approved by the IRB.

Unanticipated problem (UP)

An unanticipated problem is defined as an event that meets all of the following criteria:

- 1) Unexpected in severity, nature, or frequency given the research procedures and the characteristics of the subject population (i.e., problems that are not described in this protocol or other study documents); AND
- 2) Related or possible related to participation in the research; AND
- 3) Suggests that research places subjects or others at a greater risk of harm related to the research than was previously known or recognized.

10.2 Severity assessment

The severity of all adverse events will be assessed according to the following scale:

- Mild = not requiring treatment or intervention
- Moderate = resolved with treatment/intervention
- Severe = inability to carry on normal activities and required professional medical attention

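### The adverse event severity scale in 10.2 mixes treatment need, outcome and function, so its grades overlap and some treated, unresolved events have no grade

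*Combined protocol and SAP*

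**What the plan says.** Section 10.2 (Severity assessment) sets the scope without exception: "The severity of all adverse events will be assessed according to the following scale". Three grades follow:

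- "Mild = not requiring treatment or intervention"
- "Moderate = resolved with treatment/intervention"
- "Severe = inability to carry on normal activities and required professional medical attention"

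No rule covers an event that meets two grades, and there is no residual grade for an event that meets none.

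Seriousness is handled separately in 10.1. An event is serious if, among other criteria, it is life-threatening ("Is life-threatening; OR") or leaves significant or persistent disability. The consequence does not depend on the severity grade: "If a SAE occurs, the study primary and co-primary investigators will be immediately notified and further enrollment in the study will be halted". The IRB must also be told and must approve a restart.

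The word severe appears once more in a rule for action. Section 7.2 (Subject withdrawals) stops the study intervention and calls for immediate notification "if the subject suffers a severe adverse perioperative outcome". It does not refer to 10.2.

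**The concern.** An ordinal severity scale works when all levels measure one thing and every event falls in exactly one level. Here Mild measures need for treatment, Moderate measures what happened after treatment, and Severe measures function combined with use of care. Events that are treated and resolve can satisfy two definitions. Events that are treated and persist can satisfy none.

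The complications at issue are ones the protocol itself raises. Section 9.1 lists nerve damage at the injection site and states: "Risks associated with the use of bupivacaine include allergic reaction or inadvertent intravascular injection". Section 10.3 names local anesthetic toxicity. Section 7 foresees complaints that are new or persistent at 7 days and may need imaging, a specialist or surgery.

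At stake is whether two raters would give the same event the same grade. Events are recorded by investigators or study staff (10.1). The documents describe no blinding of patients or of those who grade events; the only person described as blinded is the independent anesthesiologist who reviews the data after 15 subjects (11.2 and 12.3). Where two grades fit, the choice is left to someone who may know the arm.

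**Working it through.** The plan gives no figure to reproduce, so the check is a logical one: list every combination of the attributes that 10.2 uses and apply the three definitions.

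**Attributes (each yes or no).** T = treatment or intervention required. R = resolved. F = unable to carry on normal activities. P = professional medical attention required.

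**Rules, from 10.2.** Mild = not T. Moderate = T and R. Severe = F and P.

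**Assumption.** Professional attention counts as an intervention, so P without T cannot occur. Four attributes give 2 × 2 × 2 × 2 = 16 combinations. Those with P but not T number 2 × 2 = 4, which leaves 16 − 4 = 12.

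| T | R | F | P | Grade(s) met |
|---|---|---|---|---|
| no | no | no | no | Mild |
| no | no | yes | no | Mild |
| no | yes | no | no | Mild |
| no | yes | yes | no | Mild |
| yes | no | no | no | none |
| yes | no | no | yes | none |
| yes | no | yes | no | none |
| yes | no | yes | yes | Severe |
| yes | yes | no | no | Moderate |
| yes | yes | no | yes | Moderate |
| yes | yes | yes | no | Moderate |
| yes | yes | yes | yes | Moderate and Severe |

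**Result.** One grade: 4 Mild + 3 Moderate + 1 Severe = 8. Two grades: 1. No grade: 3. Total 8 + 1 + 3 = 12.

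**Without the assumption.** The other 4 profiles (P but not T) return. The 2 with F = no are Mild. The 2 with F = yes meet both Mild and Severe. Of 16 profiles, 8 + 2 = 10 have one grade, 1 + 2 = 3 have two, and 3 have none. The overlap widens and the gap is unchanged.

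**Applied to complications that the protocol raises.**

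- Local anesthetic toxicity that incapacitates, needs professional attention, is treated and resolves is the last row: Moderate and Severe both fit.
- A sensory deficit from nerve injury that is treated, persists and does not stop normal activities is in the fifth or sixth row: no grade fits.
- An incapacitating event that requires no treatment is in the second or fourth row: Mild.

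Because Moderate requires resolution, the grade can also depend on when the rater looks. A treated, non-incapacitating event has no grade while it lasts and becomes Moderate once it resolves.

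**The case against.** The strongest reply is that 10.1 already does the important work. A life-threatening or persistently disabling event is serious whatever its 10.2 grade, with notification, an enrollment halt and IRB involvement. This stands, and it limits the consequence.

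A reader might infer from the Moderate definition that a life-threatening block complication which resolves with treatment is graded only Moderate. The text does not support that. The Severe definition does not exclude resolved events, so an incapacitating event needing professional attention meets it too. Moderate alone would follow only if the rater judged the functional criterion unmet, for example for a brief event just before or during anesthesia; 10.2 does not settle this.

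A reader might also infer that the scale decides whether the action in 7.2 is triggered. That section speaks of an outcome rather than an adverse event and cites no scale, so the link is open rather than established.

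Two further readings go too far. One is that an untreated deficit is Mild however disabling: the criterion is that treatment is not required, which differs from its not being given, and a persistently disabling deficit is a serious event in any case. The other is that limitation from the surgery itself would push trivial events up to Severe: the natural reading is incapacity caused by the event, and the documents give no figures on postoperative limitation.

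It can also be said that adverse event severity is not an outcome in section 2, that section 8 plans no analysis of it, and that 9.1 calls these effects extremely rare. All true. But 10.2 still demands a grade for every event, and the seriousness rules do not supply one for a non-serious event that fits no level.

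**Conclusion.** The concern holds as a defect in a stated rule. The grades in 10.2 are neither mutually exclusive (1 of 12 profiles meets two) nor exhaustive (3 of 12 meet none). The 12 rest on counting professional attention as an intervention; without that, 3 of 16 meet two and 3 of 16 meet none. These are counts of logical possibilities, not estimates of how often misgrading will happen, and the documents give no event rates from which to estimate that. One patient is 1/24 = 4.2% of an arm of 24 (8.1), which is only the weight of a single patient.

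The effect is confined to the severity grading of adverse events and its consistency between raters. The absence of any described blinding of patients or graders makes that consistency harder to defend; it does not show that grading would differ by arm. The primary outcome, the sample size and the handling of serious events are untouched.

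**What to change.** Replace 10.2 with one intensity axis judged at the worst point of the event, for example: no interference, some interference, or prevention of usual postoperative function because of the event. Wording that ties the limitation to the event keeps ordinary surgical recovery out of the grade. Record treatment given (yes/no) and outcome (resolved, ongoing, with sequelae) as separate fields on the case report form, so that nothing now captured by the mixed scale is lost.

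A smaller repair would be a tie-break line plus a category for treated, unresolved events. It closes the gap and the overlap shown above but leaves the levels measuring different things.

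Separately, the sponsor should reconcile the word severe in 7.2 with the 10.2 grade and the 10.1 definition of a serious event, by stating whether they mean the same thing. No stopping rule is proposed here.

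The cost is a short wording change and two case report form fields, with no added visits or staff. Graders still have to judge how far an event, rather than the operation, limits the patient.
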